### 5.4.1 PROMIS

The Patient–Reported Outcome Measurement Information System (PROMIS®), funded by the National Institutes of Health to provides clinicians and researchers access to efficient, precise, valid, and responsive parent– and child–reported measures of health and well–being.

### 5.4.2 Distress Rating Tool

All patients ages 12 years or older will complete the Distress Thermometer. The Distress Thermometer takes less than 5 minutes to complete.

## 5.5 ON-STUDY EVALUATION

### 5.5.1 Baseline Assessment

Laboratory values must be no older than 72 hours from the time of eligibility evaluation and starting therapy. Imaging studies must be no older than 4 weeks of enrollment at enrollment. Testing outside of this window must be repeated prior to starting study drug.

If a post-enrollment/pre-treatment laboratory value is outside of the limits of eligibility, this laboratory value must return to the eligibility requirement prior to initiating therapy. If the laboratory value does not return to the limits of eligibility within 14 days, patient may not receive protocol therapy.

The evaluations required prior to starting treatment portion of the study are listed in Section 5.6, Study Calendar. Screening labs will be repeated if they are older than 72 hours.

## 5.6 STUDY CALENDAR

Procedure	Screening	Baseline	Cycle 1 ( $\pm 3$ days)				Subsequent Cycles ( $\pm 3$ days)	Post Therapy Follow-up (approximately 30 days after final dose of study drug)
			Day 1	Day 2-5	Day 7	Day 14		
History	X						X	
Physical Exam	X	X a					X	
Vital signs	X	X	X i				X	
Performance Score	X	X a						
SGI-110 Administration			X	X			X	
Labs								
• Complete blood count with diff, platelets								
• Electrolytes (including sodium, potassium, chloride, CO 2 ), calcium, phosphorus, magnesium, creatinine, BUN, glucose, ALT, bilirubin, urinalysis, total protein, albumin, and CPK		X	X a				X	
Serum normetanephrine and metanephrine (if possible, urine), and chromogranin A (in patients with PHEO/PGL only)			X				X j	

Procedure	Screening	Baseline	Cycle 1 ( $\pm$ 3 days)			Subsequent Cycles ( $\pm$ 3 days)			Post Therapy Follow-up (approximately 30 days after final dose of study drug)
			Day 1	Day 2-5	Day 7	Day 14	Day 28	Day 1-5	
Urine/serum pregnancy test for all females of childbearing potential	X								X k
Biopsies	X c								X g
1) Tumor expression of SDH complex subunits and FH by IHC	X								X g
2) Tumor expression of NY-ESO-1 by IHC	X f								X g
LINE-1 demethylation analysis ([name] research)	X					X			
Pharmacokinetic testing	X	X d	X d						
Pharmacodynamic testing e	X				X	X	X		
Response evaluation of disease b	X	X b							X b
Quality of Life (Distress thermometer and PROMIS)	X								X h
Adverse Events	X								X
Concomitant Medications		X							X

a Laboratory tests older than 2 weeks (14 days) at the start of therapy must be repeated. For abnormal test results, refer to Section 4.2.

b Imaging studies will be repeated if older than 4 weeks at the start of therapy. Imaging evaluation selection may include CT and/or MRI, and/or FDG-PET as clinically indicated. Staging should be performed prior to the second cycle and then prior to every other cycle. The same imaging strategy will be used throughout study participation for tumor evaluation.

c when archival tissue is not available.

d active metabolite (decitabine) will be assayed in plasma prior to first dose in cycle 1 and at 0.5 hour (+/- 15 minutes), 1 hour (+/- 15 minutes), 2 hour (+/- 30 minutes), 4 hour (+/- 30 minutes), 6 hour (+/- 1 hour) and 24 hours (+/- 2 hours) after the first dose of drug in Cycle 1.

e LINE-1 demethylation in PBMC using pyrosequencing and urine and plasma glycolytic metabolites at baseline and day 7, 14, and 28 of cycle 1.

f pre-treatment tumor samples on archival tissue may be used for initial NY-ESO-1 evaluation.

g On-treatment biopsy will be performed when a core biopsy may be safely performed in consenting patients  $\geq 18$  years of age. On treatment biopsy will be optional.

h at the end of cycle 4 and then every 4 cycles thereafter (e.g. at the end of cycle 8, 12, 16, etc.), and at the end of therapy.

iVital signs will be obtained on day 1 per section **5.2**.

jAt each restaging timepoint

kPrior to each cycle

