Patients with platinum-resistant ovarian cancer were enrolled on a phase II combination trial of SGI-110 and carboplatin (NCT01696032). In combination with carboplatin a starting dose of SGI-110 of 45mg/m^2/day Daily x5 was not tolerated and the dose was de-escalated to 30mg/m^2/day. Dose of SGI-110 of 30mg/m^2/day + carboplatin AUC 4 was well-tolerated and is being used for stage II of the study. In patients with HCC, a Phase II study of monotherapy with SGI-110 is ongoing (NCT01752933). Dosing started at 60mg/m^2/day on days 1-5 every 28 days. This dose was reduced to 45mg/m^2/day Daily x5 due to grade >=3 hematological toxicity. Thirty-six subjects received this dose on stage 2 of this study. Overall, 22 of 50 subjects (44%) had SAEs in this study. Most subjects had SAEs considered not related to study treatment. No SAE with an outcome of death was considered related to study treatment.

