## 5 STUDY IMPLEMENTATION

### 5.1 STUDY DESIGN

This is a single site, open label, phase II study design using a small optimal two-stage design to evaluate the clinical response in three groups of patients:

1. wild-type GIST (GIST without Kit or PDGFRA mutation)
2. PHEO/PGL in patients with germline SDH subunit mutation (SDH deficient PHEO/PGL), or
3. RCC associated with HLRCC

Adults and children (greater than or equal to 12 years of age) with measurable localized or metastatic or unresectable wild-type GIST, SDH deficient PHEO/PGL, or HLRCC-associated

RCC will be eligible for trial participation. SGI-110 will be administered subcutaneously at 45mg/m^2/day x 5days on a 28-day cycle. Cycles may be repeated until there is evidence of tumor progression clinically or by RECISTv1.1 or there is intolerable toxicity that is not alleviated by dose reduction.

SGI-110 activity will be assessed by radiographic response of measurable disease using RECISTv1.1. Patients will be carefully monitored for toxicity and response. Time to progression, overall survival and quality of life will be evaluated as secondary objectives.

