## 5.2 DRUG ADMINISTRATION

SGI-110 will be administered subcutaneously, preferably in the abdominal area at 45mg/m^2/day x 5 days on a 28-day cycle. SGI-110 is available in a two-vial system, (1) SGI-110 for Injection 100 mg, and (2) SGI-110 Diluent for Reconstitution 3 mL.

SGI-110 drug product admixed with the custom diluent as described in section 15.1. The reconstituted SGI-110 solution is stable for 1 week under refrigerated conditions.

SGI-110 should be injected slowly (up to one minute) as some injection site discomfort or pain may be experienced. Care must be taken to avoid intradermal injection as this may result in injection site pain. To prevent injection site pain, patient should be directed to apply ice packs to the injection site before and after the injection. If the injection pain continues despite these measures, pre-treatment with topical or systemic analgesics may be considered. Patients will be observed in clinic for at least one hour after the first dose of SGI-110. Vital signs including blood pressure, heart rate, and respiratory rate will be obtained and injection site will be monitored for signs of local reaction every 20-30 minutes in clinic for 1-hour post injection after the initial dose of SGI-110.

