## 5.3 DOSE MODIFICATIONS

Although not a phase 1 study, toxicity will be evaluated and treatment limited by the toxicities defined below. This study will utilize the CTEP Common Terminology Criteria for Adverse Events (CTCAE) Version 5.0 for toxicity and Adverse Event grading and reporting. An adverse event must be judged to be possibly, probably, or definitely related to SGI-110 to be a treatment limiting toxicity. Because it is possible that longer-term administration of the drug may be required in these patient populations, two dose reductions of approximately 30% will be allowed for patients who develop toxicity determined to be treatment related.

If a subject misses or skips a dose the dose will be given the next day. When a missed or skipped dose occurs, the research team should be notified to provide guidelines to the subject on whether to proceed with further doses.

SGI-110 will be held for treatment-limiting toxicities and re-started at the reduced dose after resolution of toxicity to a grade 1 or baseline.

Treatment-limiting toxicity is defined as:

- Toxicities that are possibly, probably or definitely related to SGI-110 and are  $\geq$  grade 3, **unless** the toxicity resolves/reversible within 72 hours with supportive care.
- In addition, persistent grade 2 toxicities will be considered dose-limiting if they are intolerable to the patient.

If the patient experiences a treatment limiting toxicity after two dose reductions, SGI-110 will be discontinued permanently.

Dose Level	Dose reduction (mg/m  /dose)	Dose reduction (%)
Dose -1	30mg/m  /dose	~30%
Dose -2	20mg/m  /dose	~30%

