## 8 MEASUREMENT OF EFFECT

For the purposes of this study, patients should be re-evaluated for response after the first 4 weeks and then every 8 weeks. In addition to a baseline scan, confirmatory scans should also be obtained 4 weeks following initial documentation of objective response.

Response and progression will be evaluated in this study using the new international criteria proposed by the revised Response Evaluation Criteria in Solid Tumors (RECIST) guideline (version 1.1) [Eur J Ca 45:228-247, 2009]. Changes in the largest diameter (unidimensional measurement) of the tumor lesions and the shortest diameter in the case of malignant lymph nodes are used in the RECIST criteria.

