8.2.3 Duration of Response

Duration of overall response: The duration of overall response is measured from the time measurement criteria are met for CR or PR (whichever is first recorded) until the first date that recurrent or progressive disease is objectively documented (taking as reference for progressive disease the smallest measurements recorded since the treatment started).

The duration of overall CR is measured from the time measurement criteria are first met for CR until the first date that progressive disease is objectively documented.

Duration of stable disease: Stable disease is measured from the start of the treatment until the criteria for progression are met, taking as reference the smallest measurements recorded since the treatment started, including the baseline measurements.

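### Restaging follows cycle number in the study calendar but weeks in Section 8, so under the calendar a dose hold of unlimited length delays scans and modestly lengthens recorded PFS.

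*Combined protocol and SAP*

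**What the plan says.** Two passages set the imaging schedule. Footnote b to the calendar in Section 5.6 states: "Staging should be performed prior to the second cycle and then prior to every other cycle". The opening of Section 8 states: "patients should be re-evaluated for response after the first 4 weeks and then every 8 weeks". Neither refers to the other.

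Drug is given for "5 days on a 28-day cycle" (Section 5.2). On toxicity, Section 5.3 states: "SGI-110 will be held for treatment-limiting toxicities and re-started at the reduced dose after resolution of toxicity to a grade 1 or baseline". Its only limit is on the number of reductions: "If the patient experiences a treatment limiting toxicity after two dose reductions, SGI-110 will be discontinued permanently". It gives no longest permitted hold, and Section 5.7.1 does not list a prolonged delay among the reasons for stopping therapy.

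Section 8.2.3 runs duration of response "until the first date that recurrent or progressive disease is objectively documented". The plan defines no event date or censoring rule for PFS. Section 12 makes PFS a secondary, descriptive outcome, reported for each stratum.

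**The concern.** Progression on imaging can be recorded only when a scan is taken. If scan dates move with dosing, the recorded date depends partly on toxicity. Under footnote b, a patient whose cycles slip is imaged later than a patient with the same tumor course and no holds. Under Section 8 both are imaged in the same weeks. Staff following the calendar and staff following Section 8 would therefore generate different PFS data from the same disease.

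Holds are foreseeable. Section 2.1.5.2 reports that a monotherapy study in hepatocellular carcinoma cut its dose from 60 to 45 mg/m²/day "due to grade >=3 hematological toxicity", and 45 mg/m²/day is the starting dose here. Section 2.1.7 expects prolonged treatment. The documents do not say how often holds occur at this dose or how long they last.

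At stake are the per-stratum PFS summaries, the date that ends duration of response, and any informal comparison of these with other data.

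**Working it through.** **1. Do the two rules agree without delay?** With 28-day cycles, the scan before cycle c falls at week 4 × (c − 1). For c = 2, 4, 6, 8, 10 this gives weeks 4, 12, 20, 28, 36. Section 8 gives weeks 4, 12, 20, 28, 36. They are identical.

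**2. What does a hold do?** Under footnote b, a hold of h weeks before cycle c moves every scan from that point on by h weeks. Section 5.3 allows two reductions before permanent discontinuation, so I take two holds.
- Two 2-week holds, before cycles 3 and 4: scans at weeks 4, 16, 24, 32.
- Two 4-week holds, before cycles 3 and 4: scans at weeks 4, 20, 28, 36.
- Under Section 8 the scans stay at weeks 4, 12, 20, 28.

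**3. Effect on mean recorded PFS.** Assumptions, none of them given in the documents:
- True progression time is exponential with median m, so S(t) = 2^(−t/m).
- Progression is recorded at the first scan at or after it occurs.
- There is no clinical progression between scans and no censoring.
- PFS is dated as Section 8.2.3 dates the end of response.

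For scans at s1, s2 and every 8 weeks after s2:

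mean = s1 + (s2 − s1) × S(s1) + 8 × S(s2) / (1 − S(8))

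With m = 12: S(4) = 0.7937, S(8) = 0.6300, S(12) = 0.5, S(16) = 0.3969, S(20) = 0.3150, and 1 − S(8) = 0.3700.
- Section 8 (4, 12, …): 4 + 8 × 0.7937 + 8 × 0.5 / 0.3700 = 21.16 weeks.
- Two 2-week holds (4, 16, …): 4 + 12 × 0.7937 + 8 × 0.3969 / 0.3700 = 22.10, a shift of 0.94.
- Two 4-week holds (4, 20, …): 4 + 16 × 0.7937 + 8 × 0.3150 / 0.3700 = 23.51, a shift of 2.35.

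The same formula gives these shifts in weeks:

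| Holds | First scans | m = 12 | m = 26 | m = 52 |
|---|---|---|---|---|
| 2 × 2 weeks, before cycles 2 and 3 | 6, 16, 24 | 0.49 | 0.27 | 0.15 |
| 2 × 2 weeks, before cycles 3 and 4 | 4, 16, 24 | 0.94 | 0.54 | 0.29 |
| 2 × 4 weeks, before cycles 2 and 3 | 8, 20, 28 | 1.21 | 0.69 | 0.38 |
| 2 × 4 weeks, before cycles 3 and 4 | 4, 20, 28 | 2.35 | 1.38 | 0.77 |

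A single hold before cycle 2, 3 or 4 gives about 0.03 to 0.4 week (2 weeks), 0.1 to 1.0 week (4 weeks) or 0.4 to 2.4 weeks (8 weeks) over the same medians. These shifts apply to patients who have the holds. A stratum mean moves by the shift times the share of such patients.

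**4. Recorded medians.** The recorded median is the first scan at or after the true median. For two 2-week holds before cycles 3 and 4, a true median of 12 weeks is recorded as 12 under Section 8 and 16 under footnote b. A true median of 14 is recorded as 20 and 16, so the direction reverses. The mean shift was upward in every scenario run; the median shift has no fixed sign.

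**5. Primary design.** For the rule of 0 of 7 then 3 of 21, early termination at a 5% response rate is 0.95^7 = 0.698 (Section 12 states 70%). Attained alpha is 0.064 and power at 30% is 0.904. None of these uses the imaging schedule.

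**The case against.** Four arguments on the other side have weight. Section 8 is the endpoint section, and scanning before a cycle does not forbid an on-time scan during a hold, so a careful site may avoid the problem. Short holds move the mean by less than a week. Section 5.1 also lets treatment end on clinical evidence: "Cycles may be repeated until there is evidence of tumor progression clinically or by RECISTv1.1". That shortens the lag wherever such progression is counted. PFS is descriptive in a single-arm trial. All of this stands and limits the size of the point. It does not settle which rule applies.

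A reader might also infer more than the documents support:
- **That median PFS rises steadily with delay.** If every cycle slipped by 0, 1 or 2 weeks, a true median of 12 weeks would be recorded as 12, 15 and 18. That pattern appears because week 12 is itself a scan date. A true median of 14 gives 20, 15 and 18; a true median of 26 gives 28, 35 and 30.
- **That every cycle slips.** That scenario raises the mean by about 0.9 to 2.0 weeks for slips of 1 to 2 weeks per cycle, but repeated treatment-limiting toxicity beyond two reductions ends treatment under Section 5.3.
- **That patients receive more drug after unseen progression.** Under footnote b at most two cycles fall between scans, with or without a hold. The added weeks are weeks off drug.
- **That strata will differ in delay.** Prior-therapy rules differ by stratum (Section 3.1.1.5.1), so a difference is possible, but no figure supports one, and no comparison between strata is planned.
- **That reading the first 7 patients is compromised.** Section 12 already foresees weeks to months to determine response and allows an accrual pause.

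**Conclusion.** The inconsistency is in the current text, and following footnote b as written makes mean recorded PFS longer in patients with dose delays. With two early holds the rise is about 0.15 to 0.9 week for 2-week holds and about 0.4 to 2.4 weeks for 4-week holds, over assumed true medians of 52 to 12 weeks. These figures rest on exponential progression, on assumed hold lengths and timing, and on no clinical progression between scans. The date that ends duration of response moves in the same way. I have not computed the net effect on duration, because onset is also read from a scan.

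The impact is modest: a secondary, descriptive endpoint is affected and the response decision rules are numerically unchanged. It is still worth correcting, because the bias depends on toxicity and is easily avoided.

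**What to change.** Reconcile the two passages by rewriting footnote b to match Section 8: imaging at 4 weeks and every 8 weeks thereafter, counted from cycle 1 day 1 regardless of dose holds, delays or reductions, with a stated window in days. The confirmatory scan after a first response stays as Section 8 already has it.

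The cost is one footnote. It adds no scans beyond those Section 8 requires. The small downside is that a scan may fall within a hold instead of on a cycle visit. No change to any dose or hold rule is proposed, and no view is taken on how long a hold should last.

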## 5.7 CRITERIA FOR REMOVAL FROM PROTOCOL THERAPY AND OFF STUDY CRITERIA

Prior to removal from study, effort must be made to have all subjects complete a safety visit approximately 30 days following the last dose of study therapy.

### 5.7.1 Criteria for removal from protocol therapy

Patients participating in this study may be removed for therapy with SGI-110 due to any one of the following events:

- Completed 30-day safety follow-up period
- Progressive disease
- Participant requests to be withdrawn from active therapy
- Unacceptable Toxicity as defined in Section [5.3](#)
- Investigator discretion
- Positive pregnancy test

### 5.7.2 Off-Study Criteria

Patients who are removed from treatment permanently for any reason should be monitored until resolution or stabilization of toxicity, or until 30 days after the last dose of SGI-110, whichever is later. In addition, the following criteria will result in removal from study:

- Participant requests to be withdrawn from study
- Lost to follow up
- Death

### 5.7.3 Off Protocol Therapy and Off-Study Procedure

Authorized staff must notify Central Registration Office (CRO) when a subject is taken off protocol therapy and when a subject is taken off-study. A Participant Status Updates Form from the website (<http://home.ccr.cancer.gov/intra/eligibility/welcome.htm>) main page must be completed and sent via encrypted email to: NCI Central Registration Office [[contact]](mailto:[contact]).

Note: all minors will be kept on study and followed until the age of 18 to allow for consent.

## 6 CONCOMITANT MEDICATIONS/MEASURES

There will be no concomitant disease directed therapy allowed while patients are participating in this study.

Supportive standard therapies and preventive measures should be instituted to address known toxicities, including the following:

### 6.1 INJECTION SITE REACTIONS

Care must be taken to avoid intradermal injection, and administer by slow subcutaneous injection. If injection site pain occurs, apply ice packs to the site both before and after injection.

If injection site reactions occur despite these measures, pre-treatment with topical or systemic analgesic can be considered.

## 6.2 MUCOSITIS

To prevent mucositis, participants should be directed to increase brushing teeth with the softest tooth brush, every 4 hours and at bedtime, and rinse frequently with mouth rinses, to keep the mouth moisturized. Patients with a healthy mouth may use non-alcoholic mouthwash 4 to 6 times daily (e.g. after each meal), or according to the instructions, during the study.

Saline mouthwashes (Sodium chloride 0.9%) are preferred in cases of stomatitis, and should be used at a different time than toothbrushing (e.g. after tea).

Consider treating stomatitis at an early stage (CTCAE grade 1) or as soon as the patient complains of a sore mouth. Consider using an oral topical analgesic, with or without topical steroids, depending on the patient's clinical condition and the local standard medical practice.

## 6.3 DIARRHEA

Patients should be made aware that they may experience diarrhea, and should record the number of stools and associated symptoms. Patients should inform the physician if they develop diarrhea. The following dietary advice should be considered: BRAT diet (bananas, rice, apple sauce, toast, plain pasta), readily digestible food, avoidance of lactose-containing products and fried, fatty or spicy foods, increased fluid intake (8-10 glasses of clear fluids/day (including water, clear broth, fluids containing salt and sugar). Patients should be given loperamide to take home and should start taking loperamide after the first episode of unformed, loose stool. If diarrhea persists and after consulting with the investigator, loperamide can be continued at a dose of 2 mg every 2 hours until the patient is diarrhea-free for at least 12 hours. During the night, the patient may take 4 mg of loperamide every 4 hours. Monitor and replace fluid and electrolytes. Patients should contact their physician or study nurse if they have persistent diarrhea, diarrhea complicated by vomiting or fever, or inability to take oral liquids

# 7 BIOSPECIMEN COLLECTION

## 7.1 CORRELATIVE STUDIES FOR RES EARCH/PHARMACOKINETIC STUDIES

### 7.1.1 Pharmacokinetics

Pharmacokinetic analysis will be performed in patients during cycle 1 according to Section [5.6](#), Study Calendar. The observed decitabine  $T_{1/2}$  following SC administration of SGI-110 in adults is 2.4 hours. The active metabolite of SGI-110 (decitabine) will be assayed in plasma prior to the first dose of drug in cycle 1 and at 0.5 (+/- 15 min), 1 (+/- 15 min), 2 (+/- 30 min), 4 (+/- 30 min), 6 (+/- 1 hour), and 24 hours (+/- 2 hours). Blood samples (3mL) will be collected into 6 mL sodium heparin green top tubes. PK analysis will be performed in the laboratories of [name]. Plasma levels of decitabine will be determined using a validated liquid chromatography-mass spectrometry method.

This PK data will be used to develop a population PK model (using Phoenix NLME®, Certara, Cary, NC and RStudio) that will assess the impact of covariates including (but not limited to) age, body size (weight, height, surface area), sex, race, PD endpoints, hepatic and renal function.

The degree of change in decitabine PK based on the covariates available will be assessed to determine if dose adjustments are required.

